3. [name], Associate [name] Sciences, in the Clinical and Translational Science Institute (CTSI). She has more than ten years of experience conducting statistical methodology research, teaching, mentoring public health students, and providing consulting

services for biomedical research. She is serving as Program Director of the Biomedical Data Science Certificate Program co-sponsored by CTSI and Department of Public Health Sciences. She also serves as the Biostatistics and Informatics Core Director of an FDA/NCI funded 19 million U54 center grant on flavored tobacco products. For her biostatistics methodology research, she has worked on both genetic and genomic data analysis (gene expression, SNP, DNA methylation, ChIP-seq, ATAC-seq, and proteomics) for more than ten years, and has developed new statistical analysis methods and corresponding analysis packages in R/Bioconductor for DNA methylation array and RNA-Seq data analysis. She also developed a new method and R package to control for multiple testing error rates in genomic and genetic data analysis.

The DSMB will meet at the beginning of the randomized trial, every 3 months thereafter, and at the conclusion of the trial, or sooner if there are unanticipated side effects and adverse events. The DSMB will follow the NIH National Center for Research Resources guidelines including:

1. Review subject recruitment, attrition, and minority involvement
2. Monitor safety of research participants by reviewing unblinded data for side effects and adverse events
3. Assuring compliance with requirements relating to reporting of adverse events
4. Assuring data accuracy and protocol compliance, and that any action that results in the temporary or permanent suspension of the protocol is reported to all appropriate monitoring bodies, including the IRB, and the NIH Office of Biotechnology Activities.

Should any serious adverse event occur, we will convene a meeting with the DSMB to determine whether the study should be suspended until additional review can be properly performed.

## **18. DATA ANALYSIS PLAN – To be performed at UVA**

### Data harmonization, management and analysis

1. Develop data management and statistical analysis plan.
2. Work with the team and CTSI at URMU closely to design a unified management system for data collection, transfer between the study site and management.
3. Data oversight and monitoring during data collection and integration.
4. Harmonize the study data elements and variables from clinical and laboratory and biochemical data
5. Validate data quality and perform cleaning process.
6. Work closely with the PI and clinical investigators to determine appropriate statistical methods and machine learning algorithms for the clinical hypotheses. Cutting-edge statistical methods and innovative data science tools will be considered or adopted.
7. Prepare the analytical datasets and perform pre-stated statistical analyses.
8. Prepare the final results for manuscript writing and submission, conference presentations and publications.

**Power calculation:** The primary outcome of interest in this study is plasma 8-isoprostane, one of the markers of oxidative stress. Based on: 1) the inverse correlation between 8-isoprostane and eGFR (Figure 1 of Cottone *et al.*), 2) the average 8-isoprostane for hypertensive patients of  $262 \pm 137$  pg/ml, 3) a range from 350 to 550 pg/ml for CKD Stages 3-4 patients, and 4) therefore the assumption that the average 8-isoprostane would be  $400 \pm 150$  pg/ml in placebo group, we hypothesize that Avmacol ES would reduce by 25%, approximately at 300 pg/mL.

According to power calculations, the minimum number of participants that need to be recruited is 88. To address the challenges of recruiting patients with stage 4 CKD, there will not be a fixed proportion of patients with CKD stage 3 and 4 that will make up the final 88. However, an equal number of subjects

regardless of CKD stage (44 each) will be assigned by the IDS to the Avmacol ES and placebo arm of the study. **The final 88 will include the ones already enrolled.**

If study participants drop out, additional patients with CKD stage 3 or 4 will be recruited to reach this number. For example, if 8 out of 88 participants drop out, 8 more would be enrolled so the final number of enrollments would be 96.

If a CKD stage 4 patient drops out, a CKD stage 3 patient may be enrolled to make up for the drop-out to reach the total of 88 study participants. Treatment assignments will be performed by the IDS, and the study team will remain blinded.

With 44 patients in Avmacol ES group and 44 in placebo group who would complete the study, we expect to have power to detect the difference in 8-isoprostane between the two groups. The power analysis was performed using two-sample *t*-test with 5% type I error. The effect size is considered close to medium effect, which is appropriate for this pilot study as we intend to establish preliminary evidence of treatment effect of Avmacol ES. As mentioned above, *the Kidney Clinic in AC3 sees ~ 800-900 patients with CKD a month and ~ 60% of patients are in the CKD Stages 3-4 stages. Thus, in addition to Highland Hospital, we should be able to easily achieve our recruitment target.*

In the event that patients drop out the study due to relocation or loss to follow up, we will recruit additional patients. Based on the number of dropouts at 12 months into the study, we will recruit an extra number of patients commensurate with the dropout rate such that we will have the anticipated number of patients (44 in each group) who will complete the study in 24 months.

**Statistical Analysis:** The data for safety and feasibility assessment will be summarized descriptively with respect to adverse events and compliance with Avmacol ES intake. The difference between the two treatment groups will be evaluated with Chi-square test, and logistic regression if necessary. Distributions of outcome variables will be examined graphically for asymmetry and for outliers. If a lack of symmetry is noted, the variable will be transformed before analysis. The group-specific data will be summarized and reported as mean  $\pm$  SD or median (interquartile range) for continuous measures and as frequency and percentage for categorical measures and their differences will be compared using two-sample *t*-tests or Chi-square test. Those baseline characteristics that are significantly different between the 2 groups will be adjusted in the subsequent analyses. Since plasma 8-isoprostane will be measured at baseline, 1, 3, and 6 months, the effect of Avmacol will be explored at each time point with *t*-test or linear regression to detect an early effect of Avmacol at 1 or 3 months and to determine if such effect will be sustained at 6 months while the patients remain on Avmacol. The effect of Avmacol on longitudinal plasma 8-isoprostane measures will be analyzed with linear mixed effects model, adjusting for potential confounding factors such as age, initial BMI, and baseline characteristics identified in the preliminary analysis. Other factors that might affect the results (such as physical activity and dietary intake) will also be examined. Similar analyses will be performed for the secondary outcomes, including plasma IL-6, urine 8-isoprostane, and urine nephrin. We will also explore the effect of Avmacol on eGFR with linear mixed effects modeling by comparing the slope of eGFR decline between groups, and to the previous 6 months within group, and the effect of *GSTM1* genotype on the response to Avmacol. Additionally, penalized regression and machine learning methods such as random forests algorithm will be considered and applied to fully evaluate the treatment effect and predictability of Avmacol and other important predictors on the outcomes.

The data for safety and feasibility assessment will be summarized descriptively with respect to adverse events and compliance with Avmacol ES intake. The group-specific data will be summarized and reported as mean  $\pm$  SD for continuous measures and as frequency and percentage for categorical measures and their differences will be compared using two-sample *t*-tests or Chi-square test.

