- Our research coordinator will use eRecord EMR to screen patients for enrollment based on inclusion and exclusion criteria listed above in section #5. Each week, the research coordinator (RC) will screen subjects scheduled to visit to Kidney Clinic within the upcoming 4 weeks for enrollment. The RC will discuss with [name], who will make the final decision for inclusion and exclusion.
- The pre-screening data for potential subjects who choose not to participate or are ineligible will be deleted.

3. Informed consent and buccal swab for *GSTM1* genotyping: Buccal (cheek) swab sample will be obtained from subject: To extract DNA for *GSTM1* genotyping to assess the effect of *GSTM1* genotype on clinical and biochemical response. Genotyping will be performed as previously done. Each study participant will be assigned a subject ID by the RC after obtaining informed consent. The testing supplies for the buccal swab will be labeled by subject ID only and the lab will perform the genotyping.

3. Randomization: Randomization will be performed by the Investigational Drug Service (IDS) who will be provided the patients' CKD stage. The investigators and subjects will be blinded to the randomization of the study supplement and placebo.

At the onset, the IDS will be provided the CKD stage of each study participant (Stage 3 eGFR 30 - < 60 ml/min/1.73 m^2, Stage 4  $\geq$  20 – 29 ml/min/1.73 m^2), The URM Clinical Research Pharmacy and IDS will assist us in the randomization and dispensing process (their efforts are included in the NIH budget). The research team, healthcare providers and participants will be blinded to treatment assignment. Based on our patient mix in our clinic, we expect ~ 60% will be Caucasian, 40% will be AA, and ~ 50% will be female in each group.

While randomization will not be determined by *GSTM1* genotype, we will explore the effect of the genotype on response to treatment. After consent, *GSTM1* genotype will be determined from DNA extracted from buccal swab at a routine clinic visit. *GSTM1* genotype is for research purpose only and will be performed in [name] laboratory using established protocol 

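### Replacing drop-outs to reach 44 completers per arm, with stage 3 allowed in place of stage 4, implies steering replacements by arm; the use of CKD stage in allocation is left unclear

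*Combined protocol and SAP*

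**What the plan says.** Section 8 (Study Procedures, Randomization) has the IDS perform the randomisation and states that "the IDS will be provided the CKD stage of each study participant", with eGFR cut-offs for stages 3 and 4. It describes no strata, blocks or minimisation, and gives no purpose for the information.

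Section 18 (Power calculation) says that "there will not be a fixed proportion of patients with CKD stage 3 and 4 that will make up the final 88". It then sets arms of the same size, in which participants "regardless of CKD stage (44 each) will be assigned by the IDS to the Avmacol ES and placebo arm of the study".

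On drop-outs, the same section says "If a CKD stage 4 patient drops out, a CKD stage 3 patient may be enrolled to make up for the drop-out", and sets the recruitment goal so that "we will have the anticipated number of patients (44 in each group) who will complete the study in 24 months". Sections 4.1 and 13 also call for replacement. No passage says how a replacement's arm is chosen, beyond leaving assignment to the IDS.

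The planning assumptions for the primary outcome, plasma 8-isoprostane, rest on "the inverse correlation between 8-isoprostane and eGFR" and on "a range from 350 to 550 pg/ml for CKD Stages 3-4 patients".

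Section 18 (Statistical Analysis) adjusts for baseline characteristics that differ significantly between the groups. Age and initial BMI are named for the mixed model; CKD stage, eGFR and baseline 8-isoprostane are not. No analysis set is defined.

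**The concern.** If every arm must finish with 44 completers, a vacancy in one arm can be filled only by a patient placed in that arm. Such a patient has not been randomised between treatments. When the vacancy was left by a stage-4 patient and is filled by a stage-3 patient, the protocol's own reasoning says that the arm's expected 8-isoprostane falls with no drug effect.

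Losses that differ by arm are foreseeable. Section 13 withdraws patients whose side effects persist after dose reduction, and section 9 names gastrointestinal effects as the most common. The analysis plan may not correct the resulting imbalance, because adjustment depends on a significance test at baseline. At stake is the fairness of the primary comparison, and the ability to say afterwards how each of the 88 was allocated.

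**Working it through.** **The plan's own figure.** Inputs from section 18: placebo mean 400, SD 150, target difference 100 pg/mL, two-sample t-test at 5% (two-sided assumed). No power is stated, so the 88 cannot be reproduced as such. The t-test needs 37 per arm for 80% power and 49 for 90%; 44 per arm gives 87%. The sample size is adequate for its inputs and is not the issue.

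**Assumed inputs (not in the documents).**
- Stage-4 share: 13 of 44 in each arm (about 30%).
- Stage 4 minus stage 3 difference D: 100 pg/mL, range 50 to 150. The protocol's range for stages 3-4 is 550 - 350 = 200 wide, with no stage-specific means.
- Six stage-4 patients lost from one arm and none from the other. The protocol's example has 8 drop-outs in the whole trial.
- No drug effect, drop-outs excluded, no adjustment for stage or baseline.

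**Shift = D × (difference between arms in stage-4 share).**

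| Situation | Stage-4 shares | D = 50 | D = 100 | D = 150 |
|---|---|---|---|---|
| Loss only, no replacement | 13/44 v 7/38 | 5.6 | 11.1 | 16.7 |
| Six stage-3 replacements in the same arm | 13/44 v 7/44 | 6.8 | 13.6 | 20.5 |
| Six stage-3 replacements split 3 and 3 by randomisation | 13/47 v 7/41 | 5.3 | 10.6 | 15.9 |

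At D = 100 same-arm replacement adds 13.6 - 11.1 = 2.5 pg/mL to the loss alone. Randomising the replacements removes 13.6 - 10.6 = 3.0. Most of the shift comes from the unequal loss.

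**False-positive rate.** SE = 150 × √(2/44) = 32.0 pg/mL. From the noncentral t with 86 df, a shift of 13.6 raises the two-sided rate from 5% to about 7% (5.5% at D = 50, 9.7% at D = 150). The smallest significant difference is about 64 pg/mL.

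**How extreme is six?** If 8 of 88 drop out irrespective of arm and stage, the chance that at least six come from the 13 stage-4 patients of one given arm is hypergeometric: about 0.00008.

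**Would the baseline test catch it?** For 13/44 v 7/44, chi-square without continuity correction gives p = 0.13. Stage would not enter the model under the significance rule.

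**Does adjustment work?** A simulation assumed 18 of 44 stage 4 per arm, a baseline-to-follow-up correlation of 0.6, 4 or 8 swaps, and D of 100 or 200. The unadjusted bias was about 10 to 36 pg/mL. With stage in the model it was within 1 pg/mL of zero; with baseline 8-isoprostane as the only covariate, about 4 to 9; with change from baseline, close to zero.

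**The case against.** The strongest reply is that the replacement rule is a small part of the problem. In the worked case it adds about 2.5 pg/mL to a shift of 11 that the losses cause by themselves, and randomising the replacements leaves 10.6 of the 13.6. That stands, and it is why a remedy limited to allocation would be incomplete.

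Four stronger readings are tempting and are not supported:

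- *Stage is sent to the IDS for stratification, and section 18 contradicts this.* Section 8 gives no purpose. The section 18 phrase follows the sentence that drops a fixed stage mix, and may mean only 44/44 overall, which is compatible with stratification. The passages are unclear together rather than in proven conflict.
- *Replacements are certainly not randomised.* No passage says that they go to the drop-out's arm. That is an inference from the per-group completer target; it is reasonable, but it is not stated.
- *The rule favours Avmacol ES.* More stage-4 loss on placebo would hide a drug effect instead. Section 2 reports a favourable side-effect profile at the chosen dose, and nothing says that stage-4 patients withdraw more often.
- *Unstratified allocation biases the trial.* With 20%, 30% or 40% stage 4, chance alone gives an imbalance of at least 10 percentage points in 19%, 24% or 38% of trials. The t-test's error rate already covers this; the cost is precision.

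The planned mixed model could also keep drop-outs' data, and a change-from-baseline comparison would remove nearly all of the shift. The plan commits to neither as the primary analysis.

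**Conclusion.** The point holds in a limited form. The documents do not say how CKD stage enters allocation, and a completer target for each arm, followed literally, steers replacements by arm on a factor linked to the primary outcome. Bias needs three conditions together: stage-4 loss that differs between arms, exclusion of drop-outs, and no adjustment for stage or baseline. Even in the near-extreme case the shift is about 14 pg/mL (7 to 20), roughly 7% to 20% of the target effect, and on average well short of significance. The size rests on an assumed stage share, stage difference and pattern of loss. The change is worth making because it is cheap and the present text leaves the allocation of replacements open to challenge.

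**What to change.** 1. In section 8 (Randomization) and section 18 (Power calculation), reconcile the wording and state that the IDS randomises 1:1 in permuted blocks within CKD stage for all remaining and replacement assignments.
2. State that each replacement, of either stage, takes the next assignment on the list for their own stage, and never the drop-out's arm as such. Replace the requirement of 44 completers in each arm with the total target. Stage-3 patients may still be recruited where stage 4 is scarce.
3. Steps 1 and 2 leave the attrition part untouched. In section 18 (Statistical Analysis), therefore, keep all randomised patients with data in the mixed model, and include CKD stage (or eGFR) and baseline 8-isoprostane as covariates whatever the baseline tests show.

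The cost is protocol wording and a list by stage, using information that the IDS already receives. The final arms may differ by a few patients; at 43 v 45 the power is still 87%. Enrolment was due to close on 15 November 2024 and the latest version date is 13 November 2024. If enrolment is essentially complete, only step 3 will have much effect; it needs no new data and can still be fixed before the analysis.

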### 4. STUDY DESIGN

#### **Aim 1. To test whether Avmacol ES will be safe and well tolerated in CKD patients.**

In the PK phase (IRB protocol study 6759), we established that 4 tablets of Avmacol ES is an appropriate and tolerable dose for CKD Stages 3-4 patients. We will enroll 88 patients from the Kidney Clinic in AC3, Highland Hospital, Brockport, St. James, and FF Thompson who have CKD stages 3-4 and a steady decline in estimated glomerular filtration rate (eGFR)  $\geq 3$  mL/min/m^2/year in the previous 12 months despite receiving standard of care. Patients will be randomized in a 1:1 Avmacol ES:placebo ratio. They will be given oral Avmacol or placebo for 6 months. Any side effects or adverse effects will be documented, and compliance to the study treatment will be monitored by tablet count at study visits. A comprehensive metabolic panel will be obtained as part of standard of care at each visit to monitor for any potential metabolic, renal or liver toxicity. The effect of *GSTM1* genotype on tolerability of Avmacol ES will be determined.

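### Aim 1 asks whether Avmacol ES is safe, but its only between-arm inference is a test of no difference, with no interval for the excess risk

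*Combined protocol and SAP*

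**What the plan says.** Section 4 heads Aim 1 "To test whether Avmacol ES will be safe and well tolerated in CKD patients", and specifies the allocation: "Patients will be randomized in a 1:1 Avmacol ES:placebo ratio".

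The Statistical Analysis paragraph of Section 18 begins with "The data for safety and feasibility assessment will be summarized descriptively with respect to adverse events and compliance with Avmacol ES intake". The next sentence gives the between-arm step: "The difference between the two treatment groups will be evaluated with Chi-square test, and logistic regression if necessary". The last paragraph of Section 18 repeats the descriptive summary and names t-tests or chi-square for group comparisons. Nothing in the available text gives a confidence interval for a difference in adverse-event risk, names the safety measures to be compared, or says how the comparison would answer Aim 1.

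The sample size of 88 is set by plasma 8-isoprostane. Its basis is "With 44 patients in Avmacol ES group and 44 in placebo group who would complete the study", and the only significance level stated belongs to that calculation ("test with 5% type I error"). No adverse-event rate appears anywhere.

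The DSMB section provides separate oversight: the board is to "Monitor safety of research participants by reviewing unblinded data for side effects and adverse events", and "The DSMB will meet at the beginning of the randomized trial, every 3 months thereafter, and at the conclusion of the trial".

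**The concern.** Aim 1 seeks a positive answer. A test of the null hypothesis of no difference has two outcomes: evidence of a difference, or no such evidence. The second is not evidence that the arms are alike, least of all when the test has little power. Percentages by arm, the other planned output, do not show how large an excess is still compatible with the data.

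Tolerability is an open question here. Section 2 reports that a higher dose was dropped in the pharmacokinetic phase, in part for gastrointestinal effects. Section 9 names gastrointestinal effects as the most common, and Section 13 lists unresolved side effects as a reason for withdrawal. If the report gives percentages and p>0.05, readers have no means of telling a reassuring result from an uninformative one.

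**Working it through.** **The plan's own figure.** There is no stated sample size, power or event rate for safety to reproduce. The 88 relates to 8-isoprostane: 400 v 300 pg/ml with SD 150 gives d = 100/150 = 0.667. With 44 per arm, power = Φ(0.667 × √(44/2) − 1.960) = Φ(3.127 − 1.960) ≈ 88% (87% by the t distribution). The target power is not stated, so the 88 is neither confirmed nor refuted. It says nothing about adverse events.

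**Inputs for the safety test.** n = 44 per arm (Section 18). Two-sided α = 0.05 is an assumption for this test. Event rates are assumed and shown over a range.

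**Power of the chi-square test.** Let x and y be the numbers with an event on placebo and Avmacol, and p̄ = (x + y)/88. Then

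χ² = ((y − x)/44)² / [p̄(1 − p̄) × 2/44].

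Exact power is the sum of Bin(x; 44, p₀) × Bin(y; 44, p₁) over all pairs with χ² > 3.841 and y > x. The normal approximation is Φ([δ − 1.96√(2p̄(1 − p̄)/44)] / √([p₀(1 − p₀) + p₁(1 − p₁)]/44)), where δ = p₁ − p₀ and p̄ = (p₀ + p₁)/2. For 10% v 20% this is Φ((0.100 − 0.149)/0.0754) = Φ(−0.65) ≈ 26%.

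| Placebo v Avmacol | Exact, uncorrected | Exact, Yates-corrected | Normal approx. |
|---|---|---|---|
| 2% v 10% | 38.1% | 14.0% | 35.0% |
| 5% v 15% | 37.9% | 19.5% | 34.4% |
| 10% v 20% | 27.0% | 15.7% | 25.7% |
| 10% v 25% | 47.8% | 33.9% | 45.6% |
| 20% v 40% | 55.2% | 44.8% | 53.6% |
| 10% v 30% | 68.2% | 55.5% | 65.5% |
| 5% v 25% | 80.4% | 66.4% | 75.6% |
| 10% v 35% | 83.7% | 74.6% | 81.3% |
| 20% v 50% | 86.4% | 80.2% | 85.2% |

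By the normal approximation, 80% power needs an Avmacol rate of 26.5%, 34.5%, 47.9% or 59.3% when the placebo rate is 5%, 10%, 20% or 30%. These are excesses of 21.5 to 29.3 points.

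**Sensitivity.** A one-sided 5% test raises the approximate power to 46.7% (5% v 15%), 36.9% (10% v 20%) and 66.0% (20% v 40%). Section 18's replacement example (96 enrolled, so 48 per arm) gives 37.0%, 27.6% and 57.2% two-sided, a gain of about 2 to 4 points.

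**What an interval would add.** Suppose 2/44 on placebo and 7/44 on Avmacol have an event (4.5% v 15.9%, a difference of 11.4 points). Then p̄ = 9/88 = 0.102 and χ² = 0.01291/0.00417 = 3.09, so p = 0.079. The Wilson limits are 1.3% to 15.1% and 7.9% to 29.4%. The Newcombe limits are

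- lower: 11.4 − √((15.9 − 7.9)² + (15.1 − 4.5)²) ≈ −1.9 points
- upper: 11.4 + √((29.4 − 15.9)² + (4.5 − 1.3)²) ≈ +25.2 points.

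The p-value says only that the difference is not significant. The interval shows that an excess of up to 25 points remains compatible with the data. Even identical observed counts leave about ±13 points (4/44 each), ±17 points (9/44 each) or ±19 points (13/44 each).

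**Events not observed.** For 0/44, solving (1 − p)⁴⁴ = 0.05 gives p = 1 − 0.05^(1/44) = 6.6% as the one-sided 95% upper bound.

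**The case against.** Three stronger readings are tempting, and the documents support none of them.

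- *The plan will treat a non-significant p-value as safety.* A reader might infer this because no other route to a conclusion is stated. But no section says how a non-significant result will be interpreted.
- *Safety rests on this one test.* It does not. The same paragraph plans a descriptive summary and optional logistic regression. Visits include a metabolic panel to look for toxicity, with repeated gastrointestinal and heart-failure questionnaires. The DSMB sees unblinded adverse-event data every three months. None of these estimates the excess risk with its uncertainty, but together they mean a safety judgement need not hang on one p-value.
- *The test would miss most excesses that matter.* The documents define neither a relevant excess nor a background rate. Excesses of 20 to 30 points are detected with 68% to 86% power in several scenarios above.

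It is also fair to say that Section 18 calls this a pilot, in which limited power for adverse events is ordinary, and that it lists development of a statistical analysis plan as a task, so intervals may be intended there. Part of the text around the DSMB section was not available. The pilot argument, however, favours estimation with intervals over a p-value, and no increase in sample size is being asked for.

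**Conclusion.** The point holds as a mismatch between aim and method. Aim 1 is framed as a test of safety, while the only between-arm inference in the available text is a test of no difference, without an interval for the excess risk. At 44 per arm and two-sided 5%, that test has about 27% to 55% power for 5% v 15%, 10% v 20% and 20% v 40%, and about 80% or more only for larger gaps such as 5% v 25% or 10% v 35%. A non-significant result would therefore say little, and could be mistaken for reassurance.

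These figures rest on assumed event rates, an assumed two-sided 5% level and the uncorrected chi-square; a continuity correction lowers them. This is a low-cost improvement to the analysis, not an error in a stated figure.

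**What to change.** In the Statistical Analysis paragraph of Section 18:

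1. Make the main Aim 1 analysis the Avmacol-minus-placebo risk difference with a two-sided 95% Newcombe or score interval, for the proportion of subjects with any adverse event, any gastrointestinal adverse event, any serious adverse event, and withdrawal for side effects.
2. For events never seen in an arm, give the exact upper bound (6.6% for 0/44, one-sided 95%).
3. Word the Aim 1 conclusion from the upper confidence limit actually obtained.
4. State that p>0.05 will not be reported as showing safety or equal tolerability. The chi-square result may stay as a secondary display.
5. State the denominator. Section 13 replaces subjects who withdraw, and the 44 per arm are completers, so the safety analysis should say that it includes everyone who took study tablets. Otherwise withdrawals for side effects drop out of the comparison.

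The cost is analysis-plan wording and one extra column in the safety tables, with no new data. The downside is a more modest safety statement, because intervals at this sample size will be wide.

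### Adjustment covariates are chosen by significance tests of baseline differences between randomised arms, and baseline 8-isoprostane and CKD stage are not fixed in the model, so precision is given up and the covariate set stays open until the data are seen

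*Combined protocol and SAP*

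**What the plan says.** The Power calculation paragraph of section 18 states: "The primary outcome of interest in this study is plasma 8-isoprostane, one of the markers of oxidative stress". It assumes a placebo mean of 400 pg/ml with SD 150, and "we hypothesize that Avmacol ES would reduce by 25%, approximately at 300 pg/mL". The rationale starts from an inverse correlation between 8-isoprostane and eGFR. On the test it says "The power analysis was performed using two-sample *t*-test with 5% type I error".

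The Statistical Analysis paragraph compares baseline characteristics between arms with t-tests or chi-square tests, and then: "Those baseline characteristics that are significantly different between the 2 groups will be adjusted in the subsequent analyses". Plasma 8-isoprostane is measured at months 0, 1, 3 and 6. Each time point is explored with a t-test or a linear regression. The longitudinal measures go into a linear mixed model, "adjusting for potential confounding factors such as age, initial BMI, and baseline characteristics identified in the preliminary analysis". Baseline 8-isoprostane, CKD stage and baseline eGFR are not named as covariates.

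Section 8, under Randomization, says of the pharmacy that randomises: "At the onset, the IDS will be provided the CKD stage of each study participant". Section 14 allows unblinding before analysis and has the groups revealed to the PI and coordinators one day after the last subject's lab visit.

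**The concern.** Under randomisation, a significant baseline difference is a chance event. It does not show that the variable predicts the outcome, and a non-significant difference does not show that the variable can be ignored. The rule therefore adjusts for whatever happened to be imbalanced and leaves out prognostic variables that happened to balance.

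Two prognostic variables are at hand. One is the baseline value of the primary outcome. The other is kidney function, which the plan's own sample-size rationale links to 8-isoprostane.

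Two things are at stake. The first is precision that the month-0 data already offer. The second is the credibility of the primary result, because the covariate set depends on the data and may be settled when the arms are known.

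**Working it through.** **Inputs from the documents.** Difference 400 − 300 = 100 pg/ml, SD 150, 44 per arm, alpha 0.05 (sidedness not stated; two-sided assumed).

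**Assumed.** The correlation r between baseline and follow-up 8-isoprostane is not given; 0.3, 0.5 and 0.7 are used. A smaller true difference of 75 pg/ml is added as a sensitivity case.

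**1. The plan's own figure.** The standardised effect is 100/150 = 0.667. No target power is stated, only that "we expect to have power to detect the difference in 8-isoprostane between the two groups", so 88 cannot be strictly reproduced. At 0.667, 80% power needs 36–37 per arm and 90% needs 48–49. With 44 per arm, the noncentrality is 100/(150 × √(2/44)) = 3.127 on 86 degrees of freedom, which gives 87% power. At 75 pg/ml it is 2.345, or 64%.

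**2. Baseline always adjusted, one visit.** The residual SD is 150 × √(1 − r²).
- r = 0.3: 143.1; r = 0.5: 129.9; r = 0.7: 107.1
- Power at 100 pg/ml: 90%, 94%, 99%
- Power at 75 pg/ml: 68%, 76%, 90%

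These powers were simulated with 100,000 trials per setting.

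**3. Adjust only if baseline differs at p < 0.05, one visit.** A variable with no true difference between arms is selected in about 5% of trials. At r = 0.5 and 100 pg/ml, power is the mixture 0.951 × 0.878 (not selected, unadjusted) + 0.049 × 0.929 (selected, adjusted) = 0.880.

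| | r = 0.3 | r = 0.5 | r = 0.7 |
|---|---|---|---|
| Power at 100, rule | 87% | 88% | 89% |
| Power at 100, always adjusted | 90% | 94% | 99% |
| Power at 75, rule | 64% | 65% | 66% |
| Power at 75, always adjusted | 68% | 76% | 90% |
| Type I error, rule | 4.7–4.8% | 4.2–4.4% | 3.6–3.7% |
| Type I error, always adjusted | 5.0% | 5.0% | 5.0% |
| Type I error if either result may be reported | 6.4% | 7.3% | 8.3% |

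The ranges for type I error under the rule are the spread over repeated simulations. The rule is conservative because trials with a large baseline imbalance, where the unadjusted test would reject too often, are the ones sent to the adjusted test. At r = 0.5: 0.95 × 4.27% + 0.05 × 4.9% = 4.3%.

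**4. Mean of three follow-up visits (compound symmetry, r = 0.5).** Without baseline the SD is 150 × √((1 + 2 × 0.5)/3) = 122.5. With baseline it is 150 × √(2/3 − 0.25) = 96.8.
- At 100 pg/ml: 96.6% without and 99.8% with baseline, a gain of about 3 points
- At 75 pg/ml: 81% without and 95% with baseline, a gain of about 14 points

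**5. CKD stage (assumed 30% stage 4, stage difference 100 or 150 pg/ml, total SD 150, no stratification).** At 75 pg/ml, power is 65% or 64% without stage and 68% or 74% with it. Omitting stage leaves type I error at about 4.9%. This gain would overlap with the gain from baseline 8-isoprostane, so the two should not be added.

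**The case against.** Several stronger readings are tempting, and the documents do not support them.

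- **That baseline 8-isoprostane is excluded unless it is imbalanced.** The mixed model covers longitudinal measures that include month 0. If baseline is one of the responses and the arms share a common baseline mean, much of the precision is recovered. The plan does not say this, so the correct description is unspecified. The covariate list is also open and already names age and BMI, so selection is not by testing alone.
- **That the per-visit analyses ignore baseline.** Linear regression is offered as an alternative to the t-test, and these analyses are described as exploratory.
- **That the rule inflates false positives.** Taken literally, it does the opposite. The 6.4–8.3% figures belong to a different behaviour: choosing between adjusted and unadjusted results.
- **That stage must be modelled because randomisation was stratified by it.** Section 8 says only that the pharmacy receives the stage, and section 18 assigns 44 per arm regardless of stage. The case for including stage rests on its prognostic value alone.
- **That fixed adjustment is worth a trial of 117 patients.** 88/(1 − 0.5²) = 117 holds for one visit at r = 0.5. At r = 0.3 it is 88/0.91 = 97. Section 18 does not say whether a single visit or the mixed model is primary.

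It is also fair that the trial calls itself a pilot and that section 18 still lists developing a statistical analysis plan. At the planned effect, the loss is modest if r is low or if several visits are combined. These points limit the size of the concern. They do not defend the rule, which is stated in the plan and is not merely a gap waiting to be filled.

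**Conclusion.** The point holds. Choosing covariates by baseline significance tests discards most of the available precision, unless the mixed model uses baseline in a way that the plan does not describe. For a single visit the loss against fixed adjustment is about 3, 6 and 10 points at 100 pg/ml, and 4, 11 and 24 points at 75 pg/ml (r = 0.3, 0.5, 0.7). For the mean of three visits at r = 0.5, adjusting gains about 3 and 14 points over no baseline adjustment. All of these rest on assumed correlations, SD 150 and 44 completers per arm.

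The rule itself pulls the type I error below 5%. The risk above 5% comes from the open covariate list, the choice between t-test and regression, and permitted unblinding before analysis, taken together. The documents leave that choice possible; they do not show that it will be made. The trial is not invalidated, but the correction keeps its full value only if it is made before the groups are revealed.

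**What to change.** Delete the significance-based rule and the covariates that depend on the preliminary analysis. Before unblinding, state that every analysis of plasma 8-isoprostane adjusts for the following:
- baseline 8-isoprostane, on the scale used for the outcome
- CKD stage or continuous baseline eGFR
- age and BMI

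Use the matching baseline value for plasma IL-6, urine 8-isoprostane and urine nephrin. If the mixed model is to carry baseline as a response with a common mean, say so; it then takes the place of the baseline covariate in that model. Say also whether randomisation is stratified by CKD stage.

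All of these variables are already collected at month 0. The cost is a change of analysis wording, with no added visits, samples or patients.
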